## 15.2 Clarification of the Difference between “Severe” and “Serious”

Severity describes the intensity of an event, irrespective of its medical significance (such as severe headache). This is not the same as seriousness, which is based on regulatory definitions. Seriousness (not severity) defines SAE reporting obligations. The severity of all AEs will be graded on a 3-point scale (mild, moderate, severe) and reported in detail on the CRF.

- Mild: Discomfort noticed but no disruption of normal daily activity.
- Moderate: Discomfort sufficient to reduce or affect daily activity.
- Severe: Inability to work or perform normal daily activity.

## 15.3 AE Reporting

Specific instructions regarding the reporting of AEs, including start and stop dates, relationship to study drug, outcomes, expectedness, etc. will be detailed in the Safety Monitoring Plan.

## 15.4 Relationship to Study Treatments

“Causality” refers to the relationship of the AE to the study drug. The investigator must include assessment of causality (whether there is a reasonable possibility the drug caused the event) for each AE. Causality will be categorized according to the following criteria:

- **Not Related:** There is no medical evidence to suggest that the AE may be related to study drug usage and other causes are much more likely.
- **Unlikely Related:** There is no medical evidence to suggest that the AE may be related to study drug usage, but a relationship cannot be completely ruled out. There are other more likely causes.
- **Possibly Related:** There is weak medical evidence to suggest that the AE may be related to study drug usage and a relationship cannot be completely ruled out.
- **Likely Related:** There is good medical evidence to suggest that the AE may be related to study drug usage but other causes cannot be ruled out completely.
- **Related:** There is a strong and convincing medical evidence to suggest that the AE is related to study drug usage and other possible causes are highly unlikely.

## 15.5 Laboratory Test and Diagnostic Procedure Abnormalities

An abnormal result will not be recorded as an AE unless one or more of the below occurs:

- The abnormal test is accompanied by symptoms.
- The test result leads to an alteration or interruption in study medication.
- The test result requires medical or surgical intervention

- The test result is considered clinically significant by an Investigator.

If such an event occurs, the test should be repeated within 10 days to confirm the finding and appropriately monitored.

## **15.6 Follow-up of Adverse Events**

All AE related symptoms and/or signs will be followed until there is a return to the baseline status, all associated parameters have returned to normal (or are no longer considered clinically significant), or no further improvement is anticipated. Follow-up is mandatory, irrespective of causal relationship to the study drug(s). SAEs will be monitored until resolution, as medically indicated.

Any subject who has received at least 1 dose of the study drug and has experienced an AE that has not resolved or stabilized, may be invited to attend and unscheduled visits. Subjects with AEs that have not resolved or stabilized should be followed until resolution of the AE or for a minimum of 30 days after the subject's last application of the study medication.

## **15.7 Documentation and Reporting of Adverse Events by Investigator**

Instructions for the completion of AE reports in a clinical study are provided by the Sponsor in the Safety Monitoring Plan.

## 16. SERIOUS ADVERSE EVENTS

### 16.1 Definition

An SAE is any AE that, at any dose, results in at least one of the following outcomes:

1. Death. Death is an outcome, not an event. Where the cause of death is uncertain, the reported SAE should be the same as the term on the subject's death certificate.
2. Is life-threatening. Life-threatening means that the subject was at immediate risk of death at the time of the SAE; it does not refer to an SAE that hypothetically might have caused death if it were more severe.
3. Requires or prolongs inpatient hospitalization.
4. Persistent or significant disability or incapacity. "Persistent or significant disability or incapacity" means that there is a substantial disruption of a person's ability to carry out normal life functions.
5. A congenital anomaly or birth defect.
6. A medically serious event based upon appropriate medical judgment. Examples of such medical events include allergic bronchospasm requiring intensive treatment in an emergency room or at home, blood dyscrasias or convulsions that do not result in inpatient hospitalization, or the development of drug dependency or drug abuse.

### 16.2 Reporting of Serious Adverse Events

Full details of SAE reporting will appear in the Safety Monitoring Plan.

#### 16.2.1 Reporting of Serious Adverse Events by Investigators

If the AE is serious, the Investigator must complete an SAE Report form, in addition to the AE page in the CRF.

Any SAE, whether or not related to the study treatment, must be reported within 24 hours to the Study Medical Monitor and the CRO responsible for the site. The following contact and communication methods may be used. The Medical Monitor and CRO will confirm receipt upon receiving the notification.

## 17. STATISTICAL PLAN

### 17.1 Sample Size Rationale and Justification

The primary objective of the trial is to compare the reduction on Day 56 in the number of the AK lesions (or % reduction if baseline measure will be found different between the groups) in the Treatment Field of subjects receiving 5% or 10% VDA-1102 ointment to the reduction in the number of AK lesions in subjects receiving placebo. The sample size calculation was based on demonstrating an effect size of 0.83 using a two group t-test with a 0.045 two-sided significance level. The total significance level of 5% was divided between the interim analysis 0.5% (0.005) and the final analysis 4.5% (0.045). The sample size calculation was based on the final significance. The spending function calculation for alpha will be performed using the O'Brien-Fleming approach. Assuming a drop-out rate of 10%, approximately 84 subjects will be recruited in order to complete the study with a sample of approximately 75 evaluable subjects.

A sample size of 25 in each group will have 80% power to detect an effect size of 0.83 using a two group T-test with a 0.045 two-sided significance level.

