#### ***Interim Efficacy Analysis (IEA)***

A single interim efficacy analysis will be conducted as soon as 50% of the subjects have completed their Day 56 Visit. The objective of the IEA is to evaluate the probability of achieving the primary efficacy endpoint at the conclusion of the study. The unblinded data for the interim analysis sub-set will be analyzed by an independent statistician.

The result of the IEA will be a calculated effect size and t-value, which will be based on the difference in the change from baseline in the number of AK lesions for each of the active groups as compared to the placebo group. If baseline measure differs between the groups, then relative change (%) will be tested. The total significance level of 5% was divided between the interim efficacy analysis (0.005) and the final analysis (0.045). The spending function calculation for alpha will be performed using the O'Brien-Fleming methods. In case the distribution of the outcome variable does not approximate normality, the appropriate non-parametric methods will be considered for the interim analysis.

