## 6. STUDY OBJECTIVES

### Study Objectives:

**Primary Objective:** To compare the reduction on Day 56 in the number of the actinic keratosis (AK) lesions in the Treatment Field of subjects receiving once-daily topical 5% or 10% VDA-1102 ointment for 28 days to the reduction in the number of AK lesions in subjects receiving placebo.

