#### 17.2.1 Efficacy Analysis

The efficacy analysis will be performed with the ITT, mITT, and PP populations (see Section 17.5.2). The primary efficacy endpoint is the change from baseline in number of AK lesions. If the baseline lesions number will be found different between the treatment groups, then relative change (%) will be analyzed as well. The within-group absolute changes (decrease) in AK number of lesions from baseline to each visit will be analyzed using paired t-test or signed rank test for two means (paired observations, as is appropriate).

Comparative analysis of the above changes will be applied between each of the active groups versus the placebo group using the two-sample t-test, the non-parametric Wilcoxon-Mann-Whitney rank sum test for independent samples, or the Median test (as appropriate).

If no statistically significant differences are observed between the two active VDA-1102 groups then these two groups will be pooled and compared to the placebo group in order to achieve higher statistical power.

The overall effect and trend of differences in the changes over time between the groups will be analyzed using a mixed-effect model for repeated measures. The model will include changes from baseline at any time, the fixed effect time, and the interaction of treatment and time. Contrast will be calculated for each time point (Days 7, 14, 28, 35 and 56) versus baseline and the overall effect. The model will be adjusted for baseline measure and for other covariates suspected as affecting the outcome and which will be found different between the treatment groups.

In case the baseline number of lesions differs between the groups, analysis of relative change (%) will be applied as well.

Chi-square test or Fisher's exact test (as is appropriate) will be used for analyzing the difference in percent of subjects with complete clearance of study AK lesions at the end of the treatment. Logistic regression will be applied for analyzing the difference in proportions with adjustment for baseline measure and for other covariates suspected as affecting the outcome and which will be found different between the treatment groups.

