## 5.6.5 Efficacy Primary Analysis

- 5.6.5.1 The efficacy analysis will be performed with the ITT, mITT and PP populations (see Tables 14.2-1 - 14.2-9). The primary efficacy endpoint is the decrease from baseline in number of AK lesions. The within-group decrease in number of AK lesions from baseline to each visit will be analyzed using paired t-test or signed rank test for two means (paired observations, as is appropriate).
- 5.6.5.2 Comparative analysis of the decrease at Day 56 (mentioned above) will be applied between each of the active groups versus the placebo group using the two-sample t-test, the non-parametric Wilcoxon-Mann-Whitney rank sum test for independent samples, or the Median test (as appropriate) and using the Analysis of Covariance (ANCOVA), after optionally ranking transformation of the variable, with adjustment for sites and for other covariates suspected as affecting the outcome and which will be found different between the treatment groups.
- 5.6.5.3 Figures depicting the number of lesions by visit and by treatment group and depicting the reduction in number of lesions from Baseline to Day 56 will be generated
- 5.6.5.4 Binary variable will be defined based on the decrease in number of AK lesions at Day 56 according to a relevant cutoff (first quartile, median, third quartile or other cutoff computed by ROC curve sensitivity analysis). Comparative analysis of this variable will be applied between each of the active groups versus the placebo group using Chi-square test or Fisher's Exact test and using logistic regression with adjustment for site and for other covariates suspected as affecting the outcome and which will be found different between the treatment groups.

	DOCUMENT NUMBER: 029-BST-PLN-001	PAGE: 31 of 45
TITLE: Statistical Analysis Plan for study:  A Phase 2 Randomized, Double-Blind, Placebo-Controlled, Parallel-Cohort Study to Evaluate the Efficacy, Safety, Tolerability, and Pharmacokinetics of Once-Daily Application of Topical VDA-1102 Ointment for 28 Days in Subjects with Actinic Keratosis	EFFECTIVE DATE : 22/MAY/2017 REVISION NUMBER : 2.0	

5.6.5.5 If the two active VDA-1102 groups trend similarly then these two groups may be pooled and compared to the placebo group in order to achieve higher statistical power.

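### The 5% significance level is split between interim and final only; by inference it covers one dose-versus-placebo comparison, so error across the two-dose primary objective is neither controlled nor stated

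*Protocol*

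**What the plan says.** **Significance level.** Protocol 17.1: "The total significance level of 5% was divided between the interim analysis 0.5% (0.005) and the final analysis 4.5% (0.045". The synopsis, under Interim Efficacy Analysis, says the same: "The total significance level of 5% was divided between the interim efficacy analysis (0.005) and the final analysis (0.045". SAP 5.3.2.1 repeats the 17.1 sentence. No part of the 5% is assigned to one dose or the other.

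**Sample size.** Protocol 17.1: "A sample size of 25 in each group will have 80% power to detect an effect size of 0.83", for a two-group t-test at two-sided 0.045. SAP 5.3.2.2 agrees.

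**Comparisons.** The primary objective (Protocol 6) concerns "subjects receiving once-daily topical 5% or 10% VDA-1102 ointment for 28 days to the reduction in the number of AK lesions" on placebo. Protocol 17.2.1: "Comparative analysis of the above changes will be applied between each of the active groups versus the placebo group". SAP 5.6.5.2: "Comparative analysis of the decrease at Day 56 (mentioned above) will be applied between each of the active groups versus the placebo group". Neither analysis section states a significance level. I found no multiplicity adjustment, test order, primary dose or success rule in either document.

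**Pooling.** Protocol 17.2.1: "If no statistically significant differences are observed between the two active VDA-1102 groups then these two groups will be pooled" and compared with placebo; no level is given for the test between doses. SAP 5.6.5.5: "If the two active VDA-1102 groups trend similarly then these two groups may be pooled and compared to the placebo group"; no criterion is given. SAP 5.6.1.2 says the SAP overrides the protocol on analysis and that differences are clearly stated. This difference is not flagged.

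**The concern.** The word total invites the reading that 5% is the error rate of the primary objective. That objective contains two comparisons, and the 5% is divided over looks only. Without a success rule, the chance of declaring a benefit when neither dose works is not fixed by the plan: it depends on whether one dose or both must win, and on how the pooled test is used.

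The pooling rule adds to this. Under either document, pooling depends on how the two active arms compare, by a rule that is not fully specified. Neither document says whether the pooled test replaces the two dose tests or is added to them. A reader of the final report could not tell what error rate lies behind a positive result.

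**Working it through.** **Inputs.** From Protocol 17.1: 25 evaluable per arm, standardised effect d = 0.83, final two-sided level 0.045 (0.0225 in the favourable direction), interim level 0.005. From Protocol 7.1: 1:1:1 allocation with one placebo arm. From Protocol 17.4: interim t on 22 degrees of freedom, so about 12 per arm (12 + 12 − 2 = 22).

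**1. Which reading reproduces the stated 80%?** For a two-group t-test, df = 2 × 25 − 2 = 48 and the noncentrality is 0.83 × √(25/2) = 2.93.

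| Reading, 25 per arm | Power |
|---|---|
| One comparison at 0.045 (critical t 2.058) | 80.7% |
| One comparison at 0.0225, half the level (critical t 2.358) | 71.7% |
| Both doses significant at 0.045, both effective | 69.7% |
| At least one dose significant at 0.045, both effective | 91.7% |

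At 24 per arm the first reading gives 79.0%, so 25 is the smallest size that reaches 80%. Only the one-comparison reading matches the plan. The last two rows are simulated.

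**2. Error at the final analysis when both doses equal placebo.** The two contrasts share the placebo mean. Each has variance 2σ²/n and their covariance is σ²/n, so the correlation is 0.5. With c = z(0.9775) = 2.005:

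- Either dose, favourable: 1 − P(Z₁ ≤ c, Z₂ ≤ c) = 4.10%, against 2.25% for one test.
- Either dose, two-sided: 1 − P(|Z₁| ≤ c, |Z₂| ≤ c) = 8.20%, against 4.5%.
- Both doses: 2 × 4.50 − 8.20 = 0.80% two-sided; 2 × 2.25 − 4.10 = 0.40% favourable.

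Independent tests would give 1 − 0.955² = 8.80% two-sided, so the shared placebo arm lowers the figure slightly. A simulation of 1,000,000 null trials with t-tests (3 × 25, normal data) gives 8.17% and 4.11% for either dose, and 0.79% and 0.40% for both.

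**3. Effect of the pooled test (same simulation).** Here either dose suffices and the pooled test is also run at 0.045. Where pooling replaces the dose tests but its condition is not met, either single dose counts.

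| Use of the pooled test | Two-sided | Favourable |
|---|---|---|
| Not used | 8.2% | 4.1% |
| Added to the dose tests | 8.8% | 4.4% |
| Replaces them if both doses move the same way versus placebo (one possible reading of the SAP) | 5.3% | 2.7% |
| Replaces them if the doses differ at p ≥ 0.05 (a reading of the protocol) | 5.9% | 3.0% |
| Same, p ≥ 0.10 | 6.7% | 3.4% |
| Same, p ≥ 0.20 | 7.7% | 3.9% |

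The conditions in the last four rows are assumptions, because the documents give no level or criterion.

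**4. If the 0.005 look could also count as success** (about 12 per arm): one dose 4.7% two-sided (2.4% favourable), either dose 8.6% (4.3%). For one comparison the two looks together do stay within 5%.

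**The case against.** - **The sentence can be read correctly where it stands.** It names what is being divided, the interim and the final, and its neighbours describe one two-group test. Neither document claims control across doses. This stands: the word total is ambiguous rather than false. A reader might infer that the plan promises 5% across both doses and breaks the promise; the text does not support that.
- **The 8.2% is conditional.** It needs 0.045 per dose, which is inferred, and success on either dose, which is not stated. The 'or' in the objective may simply name the two arms. Requiring both doses gives 0.8%. So the documents do not support saying that the trial has an 8% error rate, only that the rate is not fixed.
- **Futility stopping lowers the error.** Protocol 17.4 does not call the rule binding or say which dose it applies to. If the trial stopped only when both interim t-values were below 0.34, the either-dose error would be 4.5% two-sided. The favourable-direction error would still be 4.0%, against 2.2% for one dose.
- **The SAP governs, so the protocol's pooling rule is not live.** Largely right under SAP 5.6.1.2. The three p-value rows above then matter less, but the SAP's own condition remains undefined and the change is not flagged.
- **Phase 2 trials often test doses without adjustment.** That can be acceptable and is not disputed. It calls for the level to be labelled per comparison, which the plan does not do.

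**Conclusion.** The point holds as a labelling and specification gap. The 5% is, by inference, a total over looks for one dose-versus-placebo comparison and does not cover the two-dose primary objective. If both doses equal placebo and either counts as success, the error at the final is about 8.2% two-sided (4.1% favourable). Under that same either-dose condition, the undefined role of pooling moves the two-sided figure between about 5.3% and 8.8%.

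These figures assume 25 evaluable per arm, normal data, 0.045 per comparison and, apart from the interim variant, the final analysis alone. They leave out the choice among test statistics and analysis populations. A reader might also infer that an adjustment across doses is required. The documents do not support that: they never claim such control, so whether to add it is for the sponsor to decide.

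**What to change.** 1. In Protocol 17.1, the synopsis and SAP 5.3.2.1, label 0.005 and 0.045 as levels for each dose-versus-placebo comparison. State that error is not controlled across the two doses. Disclose the either-dose error at the final: about 8% two-sided, about 4% favourable. Then either add that it is about 8.6% and 4.3% if the 0.005 look can count as success (about 12 per arm), or state that the interim is for futility only.
2. In SAP 5.6.5.5 and Protocol 17.2.1, make the pooled comparison unconditional and supportive, so that it neither replaces the two dose tests nor adds a route to success.

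**Cost.** No extra patients and no loss of power for the per-dose tests. The stated error rate looks less favourable, and the pooled test cannot carry a primary claim.

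**Not part of this fix.** Choosing a success rule or a multiplicity procedure is a design decision for the sponsor, and it does affect power. Requiring both doses gives about 70% at the assumed effect. Hochberg at 0.045 gives about 78% per dose if both work and 72% if only one does. Restoring 80% in the one-dose case takes 30 evaluable per arm: 90 evaluable, and 90 / 0.9 = 100 randomised, instead of 75 and 84. A fixed order would mean ranking two doses that the objective treats equally. The documents do not say whether the unblinded interim had been run by the SAP date of 22 May 2017; if it had, any rule added later should be dated and identified as such.

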### 17.2 Statistical analysis

All measured variables and derived parameters will be listed individually and, if appropriate, tabulated by descriptive statistics. For categorical variables summary tables will be provided giving sample size, absolute and relative frequency and 95% CI (Confidence Interval) for proportions by treatment group. For continuous variables summary tables will be provided giving sample size, arithmetic mean, standard deviation, coefficient of variation (CV%), median, minimum and maximum and 95% CI (Confidence Interval) for means of variables by treatment group. The data will be analyzed using the SAS ® version 9.3 or higher (SAS Institute, Cary North Carolina).

#### 17.2.1 Efficacy Analysis

The efficacy analysis will be performed with the ITT, mITT, and PP populations (see Section 17.5.2). The primary efficacy endpoint is the change from baseline in number of AK lesions. If the baseline lesions number will be found different between the treatment groups, then relative change (%) will be analyzed as well. The within-group absolute changes (decrease) in AK number of lesions from baseline to each visit will be analyzed using paired t-test or signed rank test for two means (paired observations, as is appropriate).

Comparative analysis of the above changes will be applied between each of the active groups versus the placebo group using the two-sample t-test, the non-parametric Wilcoxon-Mann-Whitney rank sum test for independent samples, or the Median test (as appropriate).

If no statistically significant differences are observed between the two active VDA-1102 groups then these two groups will be pooled and compared to the placebo group in order to achieve higher statistical power.

The overall effect and trend of differences in the changes over time between the groups will be analyzed using a mixed-effect model for repeated measures. The model will include changes from baseline at any time, the fixed effect time, and the interaction of treatment and time. Contrast will be calculated for each time point (Days 7, 14, 28, 35 and 56) versus baseline and the overall effect. The model will be adjusted for baseline measure and for other covariates suspected as affecting the outcome and which will be found different between the treatment groups.

In case the baseline number of lesions differs between the groups, analysis of relative change (%) will be applied as well.

Chi-square test or Fisher's exact test (as is appropriate) will be used for analyzing the difference in percent of subjects with complete clearance of study AK lesions at the end of the treatment. Logistic regression will be applied for analyzing the difference in proportions with adjustment for baseline measure and for other covariates suspected as affecting the outcome and which will be found different between the treatment groups.

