
### 11.1.5 AK Lesion Count

At the Screening and Day -1 Pre-Dose Visits, the selected Treatment Field must include at least four (4) and no more than eight (8) visible and discrete non-hyperkeratotic, non-hypertrophic AK lesions.

All AK lesions in the selected contiguous 25 cm^2 Treatment Field will be identified, counted, graded, and recorded at each visit.

If the subject has a LSR that prevents the investigator or designee from performing the AK count at a visit, the investigator or designee should document in the source document and CRF that the AK count was unable to be obtained due to a LSR.

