### **17.2.4 Exploratory Endpoints Assessment**

Chi-square test or Fisher's exact test (as is appropriate) will be used for analyzing the difference in percent of subjects with complete clearance of study AK lesions at the end of the treatment. Logistic regression will be applied for analyzing the difference in proportions with adjustment for baseline measure and for other covariates suspected as affecting the outcome and which will be found different between the treatment groups.

Sensitivity analysis will be applied for identifying the cut-off of the change (or relative change) from baseline in number of lesions on Day 56. Analysis of the difference in the binary change will be applied using Chi-square test or Fisher's exact test. Logistic regression will be applied for analyzing these differences with adjustment for baseline measure and for other covariates suspected of affecting the outcome and which will be found different between the treatment groups.

Additional exploratory endpoint assessments will be described in the Statistical Analysis Plan.

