5.6.5.6 The overall effect and trend of differences in the decrease over time between the groups will be analyzed using a mixed-effect model for repeated measures. The model will include decrease from baseline at any time, the fixed effect time, and the interaction of treatment and time. Contrast will be calculated for each time point (Days 7, 14, 28 and 56) versus baseline and the overall effect. The model will be adjusted for site and for other covariates suspected as affecting the outcome and which will be found different between the treatment groups.

5.6.5.7 For the ANCOVA analysis, logistic regression and mixed-effect model for repeated measures detailed above, if necessary, grouping of sites will be done based on similarities and differences observed between sites by post-hoc contrasts of ANOVA.

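### The other covariates enter the adjusted efficacy models only if the arms are seen to differ on them, so the model is chosen from chance imbalance and nearly all the precision those covariates could add is forgone

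*Protocol*

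**What the plan says.** Protocol 17.2.1 makes its main comparison by unadjusted tests, "between each of the active groups versus the placebo group using the two-sample t-test, the non-parametric Wilcoxon-Mann-Whitney rank sum test for independent samples"; a Median test is a further option. It then adds a mixed model and, for complete clearance, a logistic regression. The logistic model always adjusts for baseline measure, and beyond that it takes in "other covariates suspected as affecting the outcome and which will be found different between the treatment groups". The mixed-model sentence is built the same way. Baseline measure is therefore always in, and anything else must pass two conditions: suspected influence and an observed difference between arms. Protocol 17.2.4 repeats the rule for the exploratory cut-off analyses ("other covariates suspected of affecting the outcome and which will be found different between the treatment groups"). The protocol synopsis mentions baseline and other relevant covariates without the imbalance condition.

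SAP 5.6.5.2 adds an ANCOVA at Day 56 "with adjustment for sites and for other covariates suspected as affecting the outcome and which will be found different between the treatment groups". SAP 5.6.5.4 (cut-off logistic model), 5.6.5.6 (mixed model) and 5.6.6.4 (clearance logistic model) use the same rule. In the SAP the unconditional term is site, and baseline count is no longer named. SAP 5.6.1.2 gives the SAP precedence on analysis.

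Neither document lists the candidate covariates, says how a difference is to be judged, or gives the prognostic strength of any of them.

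**The concern.** Randomisation makes every baseline difference a chance event. Adjustment gains precision to the extent that a covariate predicts the outcome, and its observed imbalance says nothing about that. A rule that requires imbalance therefore selects on the wrong property: a predictive covariate that happens to be balanced is dropped.

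The rule also undermines pre-specification. A between-arm difference can be seen only with the treatment codes in hand. With no candidate list and no threshold, the content of the ANCOVA, mixed and logistic models is decided after unblinding. That matters because the ANCOVA and the mixed model sit in the SAP section on the primary efficacy analysis. In the logistic models it also matters for interpretation, since the odds ratio being estimated depends on which covariates are in the model.

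**Working it through.** **Inputs from the documents** (Protocol 17.1, SAP 5.3.2): 25 evaluable per arm, effect size 0.83 SD, two-sided 0.045, stated power 80%, 10% drop-out, 84 recruited for 75 evaluable.

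**Assumptions, not in the documents:** one normally distributed covariate; a difference is declared when a two-sample t-test of that covariate has p < 0.05; R-squared from 0.02 to 0.30. R-squared here means what the covariate adds beyond the terms already in the model, because the simulated model contains neither site nor baseline count.

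**Step 1: the plan's own figure.** Two-sample noncentral t with 25 + 25 − 2 = 48 degrees of freedom and noncentrality 0.83 × √(25/2) = 2.93 gives power 0.807 (0.790 at 24 per arm). Recruitment is 75/(1 − 0.10) = 83.3, rounded up to 84. Both reproduce. The calculation is for an unadjusted t-test and takes no credit for covariates.

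**Step 2: how often the rule admits a covariate.** Under randomisation the imbalance test rejects at its own level, so a 5% trigger admits the covariate in about 5% of trials. Simulation gave 4.9% to 5.1%.

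**Step 3: what fixed adjustment would give.** The standard error is multiplied by about √(1 − R²). Closed-form power (noncentral t, 47 degrees of freedom, effect 0.83/√(1 − R²)) is 0.847 at R² = 0.10, 0.886 at 0.20 and 0.923 at 0.30. Simulated power with fixed adjustment is slightly lower, because it includes the small cost of chance imbalance.

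| Assumed R² | SE multiplier √(1 − R²) | Power under the rule | Power, always adjusted |
|---|---|---|---|
| 0.02 | 0.990 | 81% | 81% |
| 0.05 | 0.975 | 81% | 82% |
| 0.10 | 0.949 | 81% | 84% |
| 0.20 | 0.894 | 81% | 88% |
| 0.30 | 0.837 | 82% | 92% |

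The mean standard error (never adjusted / rule / always adjusted) is 0.281 / 0.281 / 0.269 at R² = 0.10 and 0.281 / 0.280 / 0.238 at 0.30. In precision terms the rule is almost the same as never adjusting.

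**Step 4: type I error.** Under the rule it is about 4.4%, 4.1% and 3.8% at R² = 0.10, 0.20 and 0.30, against about 4.5% with fixed adjustment. Repeat simulations differ by a tenth or two of a percentage point.

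**Step 5: cost if the covariate predicts nothing.** With R² = 0, the chance imbalance inflates the variance by about 1 + 1/46, so the effective effect is 0.83/√(1 + 1/46) = 0.82. Power is then about 80%, a loss of under one point.

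**The case against.** A reader might infer four stronger things from the rule. The documents support none of them.

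- **Most of the precision available to the efficacy analysis is lost.** Baseline measure in the protocol models and site in the SAP models enter whatever the balance. If baseline explains a share Rb of the variance and the omitted covariates Rx, the share of the variance reduction lost is Rx/(Rb + Rx). That is 0.05/0.45 = 11%, 0.10/0.30 = 33% or 0.20/0.30 = 67%, depending on values that the documents do not give. Nothing shows that any candidate is a strong predictor, and eligibility restricts lesions to Grade 1 or 2 and at most 10 mm.
- **The trial is underpowered because of the rule.** The 80% belongs to the unadjusted t-test, which remains a stated comparison and to which the rule does not apply.
- **The false-positive rate is inflated.** Overall it is slightly conservative. In the roughly 9% of null trials with imbalance just short of the trigger (|t| from 1.5 to 2.0), rejection is about 7%, 8% and 10% at R² = 0.10, 0.20 and 0.30. But below the trigger the rule is the unadjusted t-test, so the two reject equally often there. This is how any unadjusted test behaves conditionally, and deleting the clause would leave the planned t-test just as it is.
- **Treatment Field location is ready for use as a covariate.** The Treatment Field Map instructions mention it only as an orientation note on a plastic sheet, and no section shows it as an eCRF variable.

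It is also fair to say that the 5% trigger is an assumption and that the gain disappears when R-squared is very small. What survives is that the rule selects on the wrong property, does so after the codes are known, and gives up almost all of whatever those covariates could add.

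**Conclusion.** The point holds as a recommendation to improve the adjusted analyses. It does not show that the planned test is invalid or underpowered. For a covariate subject to the rule, the power forgone in a continuous-outcome model is nil at R-squared 0.02, about 1 point at 0.05, 3 at 0.10, 7 at 0.20 and 10 at 0.30. These sizes rest on an assumed 5% trigger, an assumed R-squared beyond the fixed terms, 25 per arm and the planned effect of 0.83. A looser trigger would admit the covariate more often, in proportion to its level. The figures were not derived for the logistic models, where the gain would appear as power and not as a smaller standard error. The pre-specification problem does not depend on R-squared: with no candidate list and no threshold, the adjusted models are undefined until the treatment codes are open.

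The SAP makes this somewhat more pressing. Since it no longer names baseline count as a fixed term, its wording can be read as putting that variable under the imbalance rule too.

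**What to change.** In Protocol 17.2.1 and 17.2.4 and SAP 5.6.5.2, 5.6.5.4, 5.6.5.6 and 5.6.6.4, delete the second condition, the one that requires an observed difference between arms. Replace it, before unblinding, with a short fixed list entered whatever the observed balance:

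- baseline lesion count and site, the terms already unconditional in one document or the other, reconciled so that protocol and SAP name the same set;
- the Day 1 share of Grade 2 lesions, which needs no new data because lesions "will be identified, counted, graded, and recorded at each visit";
- Treatment Field location (face or scalp) only if it is confirmed to be captured in the eCRF.

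Keep the logistic models to very few terms. Baseline tables stay descriptive and do not decide any model. Bring the synopsis into line.

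The cost is wording plus one or two degrees of freedom for the added covariates, out of 48 in a pairwise comparison or 75 − 3 = 72 in a three-arm model. If the added covariate turns out not to predict the outcome, the power loss is under one point.
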